APPENDIX G – ASSESSMENT OF PRIOR AND CUMULATIVE ANTHRACYCLINE/ANTHRACENEDIONE EXPOSURE*

	Cumulative Dose Conversion		Daunorubicin isotoxic Dose Equivalent
Doxorubicin :	mg/m ²	Cumulative dose x 1.00 =	mg/m ²
Daunorubicin :	mg/m ²	Cumulative dose x 1.00 =	mg/m ²
Mitoxantrone :	mg/m ²	Cumulative dose x 4.00 =	mg/m ²
Idarubicin :	mg/m ²	Cumulative dose x 5.00 =	mg/m ²
Epirubicin :	mg/m ²	Cumulative dose x 0.67 =	mg/m ²
Patients who have received more than one anthracycline should have each individual agent cumulative dose converted to daunorubicin dose equivalents using these conversion factors, and then added together.			Total Daunorubicin Dose Equivalent: mg/m ²

* adapted from Long-Term Survivor Guidelines, Version 4.0. October, 2013 ©Children’s Oncology Group

Open label, multicenter, 3+3 cohort dose escalation of alvocidib for induction therapy combined with 7+3 cytarabine and daunorubicin, followed by optional reinduction with alvocidib combined with 5+2 cytarabine and daunorubicin and/or up to 4 cycles of consolidation therapy with high-dose cytarabine (HiDAC)

Study Populations:

Patients with newly diagnosed, previously untreated AML excluding acute promyelocytic leukemia or core-binding factor AML

Induction Therapy (alvocidib with 7+3):

- Alvocidib on Days 1-3
 - 20-mg/m² IV bolus followed by 30-mg/m² IV infusion over 4 hours, or
 - 30-mg/m² IV bolus followed by 40-mg/m² IV infusion over 4 hours, or
 - 30-mg/m² IV bolus followed by 50-mg/m² IV infusion over 4 hours, or
 - 30-mg/m² IV bolus followed by 60-mg/m² IV infusion over 4 hours
- Cytarabine 100 mg/m²/day continuous IV infusion on Days 5-11
- Daunorubicin 60-mg/m² IV bolus on Days 5-7

Optional Reinduction Therapy (alvocidib with 5+2):

- Alvocidib on Days 1-3 at the same dose used for induction
- Cytarabine 100 mg/m²/day continuous IV infusion on Days 5-9
- Daunorubicin 60-mg/m² IV bolus on Days 5-6

Optional Consolidation Therapy (HiDAC up to 4 cycles):

- Cytarabine 3 g/m² IV q12h on Days 1, 3 and 5 for a total of 6 doses
- A reduced dose of 1.5 g/m² IV q12h was permitted for patients ≥60 years old

Sample Size:

A sufficient number of patients to complete a standard 3+3 cohort dose escalation for up to 4 dose levels plus up to 20 additional patients enrolled at the maximum tolerated dose (MTD) of alvocidib

Analysis Populations:

Intent-to-treat (primary for efficacy), safety, per-protocol

Response Assessments:

Local review of bone marrow and blood test results by the investigator at the study center where patient is enrolled to classify response to treatment following to European LeukemiaNet (ELN) criteria¹

Missing Values:

Missing values will not be replaced by imputed values. Patients who do not supply bone marrow for response assessment are counted among those not achieving remission. Missing time-to-event endpoints will be censored using standard rules detailed below.

Interim Analysis:

No interim analyses. Ongoing review of clinical data performed as required for dose escalation/de-escalation decisions

Efficacy Endpoints:

CR rate (primary endpoint), combined CR rate, combined remission rate, stem cell transplant rate, overall survival, progression-free survival, relapse-free survival, CR duration

Safety Endpoints:

30- and 60-day survival, adverse events, time to neutrophil recovery, time to platelet recovery, prevalence of tumor lysis syndrome, clinical laboratory parameters, vital signs

Statistical Methods:

Descriptive statistics (including 95% confidence intervals) within and across alvocidib dose levels

2. Abbreviations

Standard abbreviations (e.g., AML = acute myeloid leukemia and mg = milligrams) are omitted intentionally.

AE Adverse Event

AML Acute Myeloid Leukemia
ANC Absolute Neutrophil Count

ATC Anatomical and Therapeutic Class

AUC Area Under Curve

BM Bone Marrow

BSA Body Surface Area
Cl Confidence Interval

CM Ara-C (Cytarabine) and Mitoxantrone

CMH Cochran-Mantel-Haenszel (test)

CR Complete Remission

CRi Complete Remission with Incomplete Blood Count Recovery

CTCAE Common Terminology Criteria for Adverse Events

DDE Drug Dictionary Enhanced

DLT Dose-Limiting Toxicity

DSMB (Independent) Data Safety Monitoring Board

ECOG Eastern Cooperative Oncology Group (performance status)

ELN European LeukemiaNet

HiDAC High-Dose Cytarabine

HR Hazards Ratio

ITT Intent-to-Treat (patient population)

IWG International Working Group

KM Kaplan-Meier (survivor function estimate)

LR Logistic Regression

MedDRA Medical Dictionary for Regulatory Activities

MRD- Minimal Residual Disease Negative

MTD Maximum Tolerated Dose

OS Overall Survival

PBSC Peripheral Blood Stem Cells
PFS Progression-Free Survival

PH Proportional Hazards (model)

PR Partial Remission

PT (MedDRA) Preferred Term

RFS Relapse-Free Survival

ROC Receiver Operating Characteristic (curve)

SAE Serious Adverse Event SAP Statistical Analysis Plan

SCT Stem Cell Transplant/Transplantation

SMQ Standardized MedDRA Query

SOC (MedDRA) System Organ Class

TEAE Treatment Emergent Adverse Event

TLS Tumor Lysis Syndrome

WHO World Health Organization

3. Definitions

Standard statistical terminology (e.g., type-1 error rate and significance level) is omitted intentionally. Efficacy endpoints are defined in Section 4.1 below (see Table 1).

Baseline Value: last measured value prior to the first dose of study drug

Combined CR: response assessment of CR or CRi

Combined Remission: response assessment of CR, CRi or PR

Cycle 1: period of time from the first dose of study drug until the start of study drug in cycle 2 or the start of alternative AML therapy other than supportive measures such as blood product transfusions (hence a patient whose first response assessment in cycle 1 is a CRi is considered to have achieved CR if neutrophils and platelets recover prior to initiation of cycle 2 or alternative AML therapy)

Combined CR Rate: percentage of patients who achieve a combined CR following treatment with alvocidib

Combined Remission Rate: percentage of patients who achieve a combined remission following treatment with alvocidib

CR Rate: percentage of patients who achieve a CR following treatment with alvocidib (see section 7.8.1)

Dose-Limiting Toxicity: Refer to the study protocol for the specific conditions and events that qualify as a dose-limiting toxicity (DLT)

Intent-to-Treat Population: all patients enrolled in the study regardless of whether they actually received study drug and regardless of whether evidence is found indicating they failed to meet study inclusion/exclusion criteria or had other protocol violations (see section 7.1)

Minimal Residual Disease Negative: Absence of gene fusion transcripts using standardized techniques such as multiparametric flow cytometry or next generation sequencing

Neutrophil Recovery: Absolute neutrophil count ≥1x10⁹/L following the administration of study drug

Per-Protocol Population: The subset of safety patients who either (a) have at least one response assessment on study, or (b) die prior to their first scheduled response assessment; however, patients are excluded from the per-protocol population if they have an important protocol deviation, such as when evidence is found indicating they failed to meet any study inclusion/exclusion criterion (see section 7.1)

Platelet Recovery: Platelet count ≥100x10⁹/L following the administration of study drug

Prestudy: Occurrence prior to the first administration of study drug

Safety Population: The subset of intent-to-treat patients who received at least one dose or partial dose of study drug (see section 7.1)

Shift Table: two-way frequency table pairing baseline value with the most extreme post-baseline result

Study Drug: alvocidib, Ara-C (cytarabine) and mitoxantrone

Treatment Failure: failing to achieve a CR, CRi or PR following induction therapy (see section 7.8.2)

4. Introduction

This Statistical Analysis Plan (SAP) details the planned methodology for summarizing data collected in the clinical study conducted under Tolero, Inc. protocol TPI-ALV-101. The current version of the study protocol is Amendment 6 dated 14-JUN-2019. Future protocol amendments (if any) will be reviewed to assess whether the changes necessitate modification of this SAP.

Since the study protocol is a companion document to this SAP, aspects in the protocol unrelated to statistical issues (e.g., patient eligibility criteria, descriptions of clinical materials, and criteria for defining treatment failure, response to treatment and disease relapse) are not repeated here.

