Once the MTD has been established, up to 20 additional patients will be enrolled at the MTD level for confirmation of safety as well as additional safety analysis and feasibility for determining MRD by dual methods (ie, MPFC and NGS) at a central laboratory.

Disease Assessment

On Day 14 (± 3 days), unless medically contraindicated, peripheral blood and bone marrow samples will be collected for disease assessment including MRD.

Patients with **no** evidence of residual leukemia ($\leq 5\%$ bone marrow blasts plus $\leq 10\%$ cellularity) will be monitored weekly and will undergo response assessment at the time of hematologic recovery (ie, absolute neutrophil count (ANC) $> 1000/\mu\text{L}$ and platelet count $> 100,000/\mu\text{L}$) or Day 50 (± 3 days), counted from Day 1 of Induction therapy, whichever occurs first. At this time, the patient may continue to Consolidation therapy with HiDAC.

Reinduction – Alvocidib and 5+2

Patients **with** evidence of residual leukemia ($> 5\%$ bone marrow blasts plus $> 10\%$ cellularity) may be eligible for a second induction cycle (or 'Reinduction') with alvocidib and 5+2 at the discretion of the Investigator. The dose of alvocidib will remain the same, but the 7+3 regimen will be changed to 5+2: cytarabine, $100 \text{ mg}/\text{m}^2/\text{day}$, as a continuous IV infusion on Days 5-9 plus daunorubicin administered at a dosage of $45 \text{ mg}/\text{m}^2$ via IV bolus of up to 15 minutes' duration on Days 5 and 6.

Should a patient undergo Reinduction therapy, they will be monitored weekly and will undergo response assessment at the time of hematologic recovery (ie, ANC $> 1000/\mu\text{L}$ and platelet count $> 100,000/\mu\text{L}$) or Day 60 (± 3 days), counted from Day 1 of Induction therapy, whichever occurs first. Upon documented hematologic recovery, the patient may continue to Consolidation therapy with HiDAC. Additional bone marrow assessments may be obtained per investigator discretion.

Investigators are permitted to administer intrathecal (IT) chemotherapy per institutional protocols after Induction (preferably during marrow aplasia), but before starting Consolidation therapy. Additional doses of IT chemotherapy may be administered after discussion with the Medical Monitor.

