4.2.3 Exclusion Criteria

Patients meeting any one of these exclusion criteria will be prohibited from participating in this study.

1. Received any previous treatment for AML
2. Diagnosed with APL-M3 or CBF-AML
3. Require concomitant chemotherapy, radiation therapy, or immunotherapy. Hydroxyurea is allowed up to the evening before starting (but not within 12 hours) of starting Induction therapy.
4. Received >200 mg/m² equivalents of daunorubicin (see [Appendix G](#) for conversion table)
5. Have a peripheral blast count of $>30,000/\text{mm}^3$ (may use hydroxyurea as in #3 above)
6. Have active central nervous system (CNS) leukemia
7. Have evidence of uncontrolled disseminated intravascular coagulation
8. Have an active, uncontrolled infection
9. Have other life-threatening illness
10. Have other active malignancies or diagnosed with other malignancies within the last 6 months, except nonmelanoma skin cancer or cervical intraepithelial neoplasia
11. Have mental deficits and/or psychiatric history that may compromise the ability to give written informed consent or to comply with the study protocol.
12. Are pregnant and/or nursing

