APPENDIX E – RESPONSE CRITERIA (2017 EUROPEAN LEUKEMIANET RECOMMENDATIONS)

Category	Definition	Comment
Response		
• CR without minimal residual disease (CR _{MRD})	If studied pre-treatment, CR with negativity for a genetic marker by real-time quantitative polymerase chain reaction (RT-qPCR), or CR with negativity by multi-color flow cytometry	Sensitivities vary by marker tested, and by method used; therefore, test used and sensitivity of the assay should be reported; analyses should be done in experienced laboratories (centralized diagnostics)
• Complete remission (CR)	Bone marrow blasts <5%; absence of circulating blasts and blasts with Auer rods; absence of extramedullary disease; absolute neutrophil count $\geq 1.0 \times 10^9/L$ (1,000/ μ L); platelet count $\geq 100 \times 10^9/L$ (100,000/ μ L)	MRD positive or unknown*
• CR with incomplete hematologic recovery (CR _i)	All CR criteria except for residual neutropenia [$<1.0 \times 10^9/L$ (1,000/ μ L)] or thrombocytopenia [$<100 \times 10^9/L$ (100,000/ μ L)]	
• Morphologic leukemia-free state (MLFS)	Bone marrow blasts <5%; absence of blasts with Auer rods; absence of extramedullary disease; no hematologic recovery required	Marrow should not merely be “aplastic”; at least 200 cells should be enumerated or cellularity should be at least 10%
• Partial remission (PR)	All hematologic criteria of CR; decrease of bone marrow blast percentage to 5% to 25%; and decrease of pretreatment bone marrow blast percentage by at least 50%	Especially important in the context of phase 1-2 clinical trials

*Including patients with morphologic CR who are MRD+ and cytogenetic and/or molecular marker positive.

2017 EUROPEAN LEUKEMIANET RECOMMENDATIONS (Cont)

Category	Definition	Comment
Treatment failure		
• Primary refractory disease	No CR or CR _i after 2 courses of intensive induction treatment; excluding patients with death in aplasia or death due to indeterminate cause	Regimens containing higher doses of cytarabine (see Table 8) are generally considered as the best option for patients not responding to a first cycle of 7+3; the likelihood of responding to such regimens is lower after failure of a first
• Death in aplasia	Deaths occurring ≥ 7 days following completion of initial treatment while cytopenic; with an aplastic or hypoplastic bone marrow obtained within 7 days of death, without evidence of persistent leukemia	

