4.1. Study Endpoints

Statistical analysis and/or summarization is planned for the following study endpoints. Complete details on how endpoints are calculated and compared across treatment arms are presented in the subsections below. A key to abbreviated terms appears in Section 2.

Table 1. Study Endpoints

Primary Efficacy Endpoint

 CR Rate: percentage of patients who achieve a CR as assessed by the investigator following treatment with alvocidib

Secondary Efficacy Endpoints (not listed in order of importance)

- CR_{MRD}
 Rate: percentage of patients who achieve a CR and test negative for minimal residual disease (MRD) using standardized techniques such as multiparametric flow cytometry or next generation sequencing
- Combined CR Rate: percentage of patients achieving a combined CR (CR or CRi) following treatment with alvocidib
- Combined Remission Rate: percentage of patients achieving a combined remission (CR, CRi or PR) following treatment with alvocidib
- Overall Survival: time from the date of first dose (Day 1) until death from any cause
- Progression-Free Survival: time from the date of first dose (Day 1) until (a) treatment failure, (b) relapse after combined remission (CR, CRi or PR), or (c) death from any cause, whichever occurs first
- Relapse-Free Survival Following CR (defined only for patients who achieve a CR during the study): time from the date of CR (Day 1) until (a) relapse after CR, or (b) death from any cause, whichever occurs first

Table 1. Study Endpoints

- Relapse-Free Survival Following Combined CR (defined only for patients who achieve a combined CR during the study): time from the earliest date of combined CR (Day 1) until (a) relapse after combined CR, or (b) death from any cause, whichever occurs first
- Relapse-Free Survival Following Combined Remission (defined only for patients who achieve a combined remission during the study): time from the earliest date of combined remission (Day 1) until (a) relapse after combined remission, or (b) death from any cause, whichever occurs first
- CR Duration (defined only for patients who achieve a CR during the study):
 time from the date of CR (Day 1) until relapse after CR
- Combined CR Duration (defined only for patients who achieve a combined CR during the study): time from the earliest date of combined CR (Day 1) until relapse after combined CR

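### The SAP defines MRD-negative by gene fusion transcripts only, which contradicts the protocol's response criteria; discordant MPFC/NGS results have no rule, and dual-method MRD feasibility has no analysis

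*SAP*

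**What the plan says.** Four texts bear on how MRD negativity is defined.

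- **SAP section 3, Definitions:** MRD-negative is "Absence of gene fusion transcripts using standardized techniques such as multiparametric flow cytometry or next generation sequencing".
- **SAP section 4.1, Table 1:** the CR_MRD- rate, a secondary efficacy endpoint, is the "percentage of patients who achieve a CR and test negative for minimal residual disease (MRD) using standardized techniques", with flow cytometry or NGS as examples. Fusions are not mentioned.
- **Protocol Appendix E:** CR without MRD is, where a marker was studied before treatment, "CR with negativity for a genetic marker by real-time quantitative polymerase chain reaction (RT-qPCR), or CR with negativity by multi-color flow cytometry". The comment against plain CR reads "MRD positive or unknown". NGS is not named.
- **SAP sections 3 and 4 (opening text):** section 3 points to Table 1 for the efficacy endpoints, and section 4 leaves the criteria for response to the protocol.

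On the two assay methods, protocol section 4.1 enrols up to 20 further patients at the MTD to confirm safety and also to study "feasibility for determining MRD by dual methods (ie, MPFC and NGS) at a central laboratory". Sections 4.3.3, 4.3.3.2 and 11.2 repeat this. SAP section 7.9 covers only MCL-1 dependence. The SAP synopsis endpoint list and the planned tables in SAP Table 3 contain no MRD or CR_MRD- entry. Protocol section 11.3.2 lists CR_MRD- as a response category and otherwise uses MRD as an example of a model covariate.

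**The concern.** CR_MRD- is a protocol response category and a SAP secondary endpoint, yet the SAP's only definition of MRD-negative is narrower than the criterion it should implement. Appendix E treats flow negativity as a route of its own, separate from any genetic marker. The section 3 wording makes flow and NGS merely ways of looking for fusion transcripts. A programmer following it would set aside a flow or NGS result that does not concern a fusion, and would have to invent a class for patients who never had a fusion to track.

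Two further gaps follow. Table 1 joins flow and NGS with an "or"-type construction and gives no rule for a patient who is positive by one and negative by the other, although protocol section 1.1.2 says that methods differ in applicability and sensitivity. And one stated reason for the expansion cohort would leave the study without a reported answer.

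**Working it through.** The documents state no CR_MRD- rate, MRD-positive share, fusion prevalence or precision target, so there is no planned figure to reproduce. The check compares the texts and then shows how far their readings diverge.

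**1. How each text treats the difficult cases**

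- *CR, flow-negative, no fusion:* negative under Appendix E and consistent with Table 1. Under section 3, either negative (no transcript is present) or not assessable (nothing to test).
- *CR, flow-positive, no fusion:* not shown negative by flow under Appendix E. Under section 3 read literally, it could be counted negative.
- *CR, no MRD result:* stays in CR under Appendix E. The missing-value rule in SAP section 7.2 covers only patients who supply no marrow. It does not cover a marrow sample without a valid MRD result.

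**2. Size of the divergence**

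Inputs:
- c = CR rate. Protocol Table 2 gives 76/109 = 69.7% and 26/56 = 46.4% for the two arms of the earlier randomised trial of FLAM against 7+3. These only set a range, because neither arm is the present regimen.
- f = share of CR patients with a trackable fusion. Not in the documents; assumed 5% to 30%.
- m = share of CR patients who are MRD-positive on an applicable assay. Not in the documents; assumed 20% to 60%.
- f and m are taken as independent.

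Results for f = 10% and m = 40%, with the span over the full assumed ranges:

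| Reading | Formula | c = 69.7% | c = 46.4% | Share of CR rate, full range |
|---|---|---|---|---|
| No fusion counts as negative | c(1 − f·m) | 66.9% | 44.6% | 82% to 99% |
| No fusion counts as not assessable | c·f·(1 − m) | 4.2% | 2.8% | 2% to 24% |
| Appendix E, every CR patient assessed | c(1 − m) | 41.8% | 27.9% | 40% to 80% |

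For c = 69.7%: 0.697 × (1 − 0.04) = 0.669; 0.697 × 0.1 × 0.6 = 0.042; 0.697 × 0.6 = 0.418. The ends of the ranges are 1 − 0.3 × 0.6 = 0.82 and 1 − 0.05 × 0.2 = 0.99; 0.05 × 0.4 = 0.02 and 0.3 × 0.8 = 0.24; 1 − 0.6 = 0.40 and 1 − 0.2 = 0.80.

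The two literal readings fall on opposite sides of the Appendix E result.

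**3. Discordant methods**

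Suppose each method calls 40% of CR patients positive (assumed), so each calls q = 60% negative. With unknown overlap, negative by either method lies between q = 60% and min(1, 2q) = 100% of CR patients. Negative by both lies between 2q − 1 = 20% and q = 60%. The choice of rule alone can therefore move the rate substantially.

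**4. What the expansion could say about feasibility**

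If all 20 patients were enrolled and the proportion with valid results by both methods were reported, the exact (Clopper-Pearson) 95% intervals would be:
- 16/20: 56.3% to 94.3%
- 18/20: 68.3% to 98.8%
- 20/20: 83.2% to 100%

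Neither document plans this summary or any measure of MPFC/NGS agreement. The SAP reference list includes a paper on an agreement coefficient, but no analysis in the text uses it.

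**The case against.** The strongest reply is that section 3 does not govern the endpoint. The SAP sends endpoint definitions to Table 1, has the investigator classify response by ELN criteria, and leaves response criteria to the protocol. On that path a patient needs a negative test, and unknown status stays in CR. This stands to a degree: a careful programmer could reach the Appendix E result. But Table 1 does not say what a negative MRD test is, section 3 is the SAP's only definition of that term, and no order of precedence is given. The contradiction remains.

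A reader might infer something stronger: that patients with no fusion are negative by default, so CR_MRD- is inflated to nearly the CR rate. The exclusion "Diagnosed with APL-M3 or CBF-AML" might seem to support this by suggesting that few enrolled patients carry a fusion. The documents do not support it. No passage classes a patient without a fusion, or without a test, as negative. The documents give no fusion prevalence and do not say that the excluded subtypes are the fusion-bearing ones. An inflation factor of 1/(1 − m), or 1.25 to 2.5 for m of 20% to 60%, holds only under that reading and as f tends to zero. The other reading sends the rate towards zero.

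It is also fair that safety confirmation is the expansion's first stated purpose, that MRD is an exploratory objective in protocol section 3, and that section 11.3.2 allows additional exploratory analyses. Those points lower the priority of the feasibility gap but do not fill it.

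**Conclusion.** The concern holds as a contradiction in a stated endpoint rule, with two related omissions. The fusion-only definition conflicts with Appendix E and does not fit Table 1. Under the assumed ranges, a literal application gives anywhere from 2% to 99% of the CR rate, against 40% to 80% under Appendix E. Those figures rest on assumed f and m, on independence between them, and on CR rates borrowed from another trial. They show that the endpoint is not fixed by the text; they do not estimate a bias, whose direction and size are undetermined.

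The missing rule for discordant results and the absent feasibility analysis hold without any assumption about prevalence.

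This should be fixed, but it does not threaten the trial's main purpose. The study is descriptive, its primary objective is safety and the MTD, protocol section 7.2 disclaims a formal efficacy analysis, and no escalation or MTD rule uses CR_MRD-.

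**What to change.** Amend the SAP before database lock:

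1. Delete the fusion-transcript wording from section 3 and align the definition with Appendix E.
2. State explicitly how NGS counts, for example as negativity for a marker present at baseline. Appendix E names only RT-qPCR and flow, so this is an addition to it. Give the assay, threshold and time point for each method.
3. Keep CR patients with no valid MRD result in the denominator as not CR_MRD-, as Appendix E already implies.
4. Report CR_MRD- by MPFC and by NGS, and state in advance whether negativity by either or by both gives the headline rate.
5. Add CR_MRD- to the planned tables, with one further table giving the proportions with valid MPFC, valid NGS and valid paired results (exact 95% CIs), and MPFC/NGS agreement.

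The cost is SAP wording and a small amount of tabulation. The samples are already scheduled in protocol sections 5.2.5, 5.2.6, 5.3.1 and 5.4.5, so no trial procedure changes. With at most 20 expansion patients the feasibility interval will be wide, and the report should say so.

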7.10.5. Neutrophil Recovery

Time to neutrophil recovery is defined for all patients and is measured from the date of first dose (Day 1) until the first day the absolute neutrophil count (ANC) is $\geq 1 \times 10^9 / L$ for 14 consecutive days. It is assumed that the ANC remains above the threshold value of $1 \times 10^9 / L$ unless there is evidence that it did not. Therefore, a patient with ANC $\geq 1 \times 10^9 / L$ on Day 45 and without another assessment for > 14 days will have a time to neutrophil recovery of 45 days.

Rules for censoring time to neutrophil recovery are:

- A patient with ANC <1x10⁹/L as of the date he is lost to follow-up will have his time to neutrophil recovery censored on the date of his last assessment of any type
- A patient with ANC <1x10⁹/L as of the database lock will have his time to neutrophil recovery censored on the date of his last assessment of any type

Summary statistics will include the number and percentage of censored times to neutrophil recovery, quartile times to neutrophil recovery, 95% Cls for the quartile times to neutrophil recovery, and KM "survival" percentages with 95% Cls at select milestone times (e.g., 42, 49 and 56 days).

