7.10.6. Platelet Recovery

Time to platelet recovery is defined for all patients and is measured from the date of first dose (Day 1) until the first day the platelet count is $\geq 100 \times 10^9 / L$ for 14 consecutive days. It is assumed that the platelet count remains above the threshold value of $100 \times 10^9 / L$ unless there is evidence that it did not. Therefore, a patient with platelet $\geq 100 \times 10^9 / L$ on Day 60 and without another assessment for >14 days will have a time to platelet recovery of 60 days.

Rules for censoring time to platelet recovery are:

- A patient with platelet count <100x10⁹/L as of the date he is lost to follow-up will
 have his time to platelet recovery censored on the date of his last assessment of
 any type
- A patient with platelet count <100x10⁹/L as of the database lock will have his time to platelet recovery censored on the date of his last assessment of any type

Summary statistics will include the number and percentage of censored times to platelet recovery, quartile times to platelet recovery, 95% CIs for the quartile times to platelet recovery, and KM "survival" percentages with 95% CIs at select milestone times (e.g., 49, 56 and 63 days).

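### The SAP's upgrade from CRi to CR does not require neutrophils and platelets to reach threshold on the same date, so a patient can be scored CR without ever meeting the protocol's CR counts together

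*SAP*

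**What the plan says.** The upgrade rule sits inside the definition of Cycle 1 in SAP Section 3. A patient whose first response assessment in that cycle is CRi is "considered to have achieved CR if neutrophils and platelets recover prior to initiation of cycle 2 or alternative AML therapy".

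The same section defines the two recoveries one by one:

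- Neutrophils: "Absolute neutrophil count ≥1x10⁹/L following the administration of study drug".
- Platelets: "Platelet count ≥100x10⁹/L following the administration of study drug".

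Neither entry sets a duration, refers to the other cell line, or requires the count to come after the marrow that was read as CRi.

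The safety endpoints define recovery differently. SAP 7.10.5 requires the neutrophil threshold to be held "for 14 consecutive days. It is assumed that the ANC remains above the threshold value of" 1×10⁹/L unless there is evidence otherwise. SAP 7.10.6 has the parallel platelet rule, "for 14 consecutive days. It is assumed that the platelet count remains above the threshold value of" 100×10⁹/L. The SAP does not link either version of recovery to the upgrade.

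Protocol Appendix E gives CR as one set of criteria: marrow blasts below 5%, "absence of circulating blasts and blasts with Auer rods; absence of extramedullary disease; absolute neutrophil count" at least 1.0×10⁹/L, and platelets at least 100×10⁹/L. The protocol's hematologic recovery, which triggers the response assessment (Protocol 5.2.6), is likewise a joint neutrophil-and-platelet condition.

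**The concern.** Appendix E treats the two counts as part of a single state of remission. The SAP's upgrade asks only that each cell line has reached its threshold at some time. A patient whose neutrophils rise and fall back before the platelets rise satisfies the upgrade but never shows the Appendix E counts together.

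The rule acts on the patients for whom this matters. Without reinduction, response is assessed at joint recovery or at Day 50, whichever is first. A CRi at that visit will typically be a patient who has not reached joint recovery.

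CR rate is the SAP's primary efficacy endpoint (SAP 4.1 and 7.8.1). Relapse-free survival following CR and CR duration (SAP 7.8.4 and 7.8.5) admit only CR patients and start at the date of CR. The SAP does not say what that date is for an upgraded patient, and this gap remains on any reading of the rule.

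**Working it through.** The plan gives no figure for this rule, so there is nothing to reproduce. The check applies three rules to invented count series and then sizes the effect of one reclassified patient.

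**Rules**

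| Rule | Source | Condition |
|---|---|---|
| Any count | SAP 3 | Some ANC ≥1.0 and some platelet count ≥100, on any dates after study drug |
| 14-day | SAP 7.10.5, 7.10.6 | Each line at threshold for 14 days, assumed to hold unless a later count contradicts it |
| Joint | Protocol Appendix E | ANC ≥1.0 and platelets ≥100 on one date |

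**Series A** (ANC and platelets in 10⁹/L)

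| Day | 36 | 43 | 50 | 57 | 64 |
|---|---|---|---|---|---|
| ANC | 0.6 | 1.2 | 0.8 | 0.7 | 0.8 |
| Platelets | 40 | 60 | 80 | 110 | 90 |

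- Any count: ANC qualifies on Day 43 and platelets on Day 57, so the patient is scored CR.
- 14-day: ANC fails on Day 50 and platelets fail on Day 64, so neither line recovers.
- Joint: met on no date.

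**Series B**

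| Day | 29 | 36 | 43 | 50 | 57 | 64 | 71 |
|---|---|---|---|---|---|---|---|
| ANC | 1.2 | 1.1 | 1.3 | 0.8 | 0.9 | 0.9 | 0.8 |
| Platelets | 40 | 55 | 70 | 90 | 110 | 120 | 115 |

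- Any count: ANC qualifies from Day 29 and platelets from Day 57, so the patient is scored CR.
- 14-day: ANC recovers on Day 29 and platelets on Day 57, so both lines recover.
- Joint: met on no date.

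The series assume that the other CR criteria are met and that the first assessment is CRi. On Day 50 both counts are low, which is CRi only if Appendix E's choice between neutropenia and thrombocytopenia is read as including both. If one count must be at threshold, place the assessment on Day 43, using an additional marrow as the protocol permits. ANC is then at threshold, platelets are not, and the results above do not change.

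Series B is the decisive case. Applying the 14-day rule to the upgrade would not close the gap, because two 14-day runs need not overlap. What is missing is the same-date condition.

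**Size of one reclassification.** The shift in CR rate is 100 × 1/n points.

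| n | Where n comes from | Shift |
|---|---|---|
| 3 | Three of the dose levels in the SAP Appendix 2 sample table | 33.3 |
| 13 | 30/60 mg/m² column of the same table | 7.7 |
| 22 | Study total in the same table | 4.5 |
| 40 | Upper planned number, Protocol 11.2 | 2.5 |

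With exact (Clopper-Pearson) 95% intervals at n=22, and starting rates assumed near the 70% and 46% that Protocol 2.6.2 reports for the randomized phase 2 study:

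- 15/22 = 68.2% (45.1 to 86.1) becomes 14/22 = 63.6% (40.7 to 82.8).
- 10/22 = 45.5% (24.4 to 67.8) becomes 9/22 = 40.9% (20.7 to 63.6).

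**The case against.** The strongest reply is that Appendix E still governs. The SAP synopsis has the investigator classify response by ELN criteria, and the primary endpoint is CR as the investigator assesses it. The upgrade is a parenthesis explaining how long a response may mature within Cycle 1. It can be read as saying that the element CRi lacked has since been met. This stands in part. The SAP does not say whether the upgrade is derived from the data or judged by the investigator, so inflation is possible, not certain. But the parenthesis is a stated scoring rule next to its own definitions of recovery, and a programmer following them would get the results above.

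It is also true that few patients may be affected. Where both counts rise and stay up, separate and joint recovery pick out the same patients and the excess is zero. Combined CR rate is unaffected, because it already includes CRi. The protocol plans no formal efficacy analysis.

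Three stronger readings are not supported:

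- **Transfusion.** Section 3 says Cycle 1 ends at "alternative AML therapy other than supportive measures such as blood product transfusions", so a reader might infer that transfused platelets produce CRs that Appendix E would refuse. Appendix E sets no transfusion condition for CR; a non-transfused count is specified only under progressive disease. One platelet count of 105 after transfusion, with ANC 1.3 on the same day, meets the Appendix E counts. Silence on transfusion is common to both documents, and no transfusion-free interval can be drawn from either.
- **Time to platelet recovery.** A reader might infer that unstable counts shorten this endpoint too. They do not: under SAP 7.10.6 a count contradicted within 14 days does not qualify.
- **Blasts.** A reader might infer that an upgraded patient could have active leukaemia unnoticed. CRi already requires the other CR criteria, hematology includes a manual differential, and blasts reappearing in blood are a relapse under Appendix E.

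**Conclusion.** The point holds as a defect in a stated rule for the SAP's primary efficacy endpoint. As written, the upgrade can score CR in a patient who never has both Appendix E counts together, and this is so under either of the SAP's definitions of recovery. CR rate, and entry to relapse-free survival and CR duration following CR, can be inflated as a result. The start date of those two endpoints is undefined for upgraded patients in any case.

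The conclusion rests on a literal reading of Section 3 and on taking the Appendix E list as a joint condition. Appendix E does not say that the counts must fall on one day, but that is the natural sense of a single list, and the protocol's joint hematologic recovery agrees with it. The number of patients affected cannot be estimated from the documents. The change should be made before the response data are analysed.

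**What to change.** In SAP Section 3, count a CRi as CR only from the first sample date that meets all of the following:

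- it is at or after the CRi assessment, and before the next cycle or alternative AML therapy;
- ANC is ≥1.0×10⁹/L and platelets are ≥100×10⁹/L in that sample;
- there are no circulating blasts and no relapse.

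Name that date as the CR date for relapse-free survival and CR duration. State that the 14-day rule in 7.10.5 and 7.10.6 applies only to the time-to-recovery safety endpoints. It would also help to say whether the upgrade is derived in programming or recorded by the investigator.

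The cost is SAP wording. The counts and differentials come from hematology that is already scheduled weekly after chemotherapy (Protocol 5.2.4, Appendix D), so no new data are needed. The downside is that the CR rate may be slightly lower.
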